10.2. Appendix 2: Time & Events

10.2.1. Protocol Defined Time & Events

10.2.1.1. Schedule of Assessments Year 1 to the End of the Study

Protocol activity (visits ±1 week, except Weeks 2 and 4 which are ±3 days) (Note: All visit timings are relative to Day 1)	Screen Week -8	Run-in Week -4	Day 1 through Week 52					
			Day 1 ¹³	Week 2	Full study visit Week 4, 16, 28, 40	Abbreviated study visit Week 8, 12, 20, 24, 32, 36, 44, 48	Week 52	Unscheduled ¹⁰
Informed Consent (main study)	X ²⁰							
IRT system transaction	X	X	X	X	X	X	X	X
Subject reminder, inform site staff of changes in health ¹			X				X	
Check/confirm entry criteria, weight	X		X					
History: medical, hospitalization, transfusion demography, height	X							
SBP/DBP, HR (single readings unless otherwise indicated)	X	X	X (triplicate)	X	X	X	X (triplicate)	X
ECG			X ¹⁷				X	
Ultrasound of kidneys and adrenal glands		X ¹⁶						
Placebo run-in or randomized treatment dispensing (start administration on day of dispensing)		X (placebo)	X	X ⁹	X	X	X	X ⁹
Placebo run-in or randomized treatment compliance			X (placebo)	X ¹¹	X	X	X	X ¹¹
Iron therapy, transfusions ²	X	X	X	X	X	X	X	X
Rescue medication(s) for Initial Intervention ^{2,3}					X	X	X	
Females only: estradiol and FSH (if required)	X							
FRP only: urine pregnancy test ^{4,18}		X	X		X		X	
HemoCue Hgb	X	X	X	X	X	X	X	X
Hematology ⁵	X	X	X		X	Hgb only	X	X
Clinical chemistry ⁵	X		X		X		X	X
Ferritin, total iron, UIBC ⁵	X		X		X		X	
Hepcidin			X		X		X	
HbA1c ⁶ , lipids (non-fasting)			X				X	
hsCRP, iPTH			X		Wk 28		X	
Urine albumin/ creatinine ratio			X		Wk 4, Wk 28		X	

CONFIDENTIAL

200808

Protocol activity (visits ±1 week, except Weeks 2 and 4 which are ±3 days) (Note: All visit timings are relative to Day 1)	Screen Week -8	Run-in Week -4	Day 1 through Week 52					
			Day 1 ¹³	Week 2	Full study visit Week 4, 16, 28, 40	Abbreviated study visit Week 8, 12, 20, 24, 32, 36, 44, 48	Week 52	Unscheduled ¹⁰
Storage biomarkers (blood, urine) ¹⁹			X		Wk 28		X	
Hospitalization ² , transition to dialysis ^{2,7} , kidney transplant ²				X	X	X	X	X
Non-serious AEs, SAEs, AEs of special interest, clinical events	X ⁸	X	X	X	X	X	X	X
Review concomitant medications	X	X	X	X	X	X	X	X

Schedule of Assessments Year 1 to End of Study (Continued)

Protocol activity (visits ±1 week) (Note: All visit timings are relative to Day 1)	Year 2				Year 3				Year 4					Unscheduled ^{10,12}	End of Study ¹⁵	Follow-up (4-6 weeks after stopping randomized treatment)	

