10.6.4.4. Adverse Events

Adverse Events
AEs of Special Interest

Adverse events of special interest are classified as follows:
 
 • Thrombosis and/or tissue ischemia secondary to excessive erythropoiesis • Cardiomyopathy • Pulmonary artery hypertension • Cancer-related mortality and tumor progression and recurrence • Esophageal and gastric erosions • Proliferative retinopathy, macular edema, choroidal neovascularization • Exacerbation of rheumatoid arthritis • Worsening of hypertension

Adverse Events

Potential AESIs will be identified through a pre-defined terms of interest process in which pre-defined lists of AE preferred terms corresponding with each AESI will be used to identify events considered to be potential AESIs. Sites will be prompted via query to complete any necessary additional information for these AESIs in the eCRF.

For the category of thrombosis and/or tissue ischemia secondary to excessive erythropoiesis, after the terms of interest list has been applied, the additional Hgb criteria described below will be applied to identify only those events that are considered to be secondary to excessive erythropoiesis as meeting the AESI definition for thrombosis and/or tissue ischemia secondary to excessive erythropoiesis.

Thrombosis and tissue ischemia events will be considered to be secondary to excessive erythropoiesis if during the window of [AE start date – 30 days, AE start date +15 days] any one of the following 3 events occurs:

- Any Hgb value \geq 13 g/dL (measured pre-dialysis)
- Hgb increase $>$ 2 g/dL over 2 weeks (+1 week)
 - Note: for programming purposes, a +1 week window is applied, corresponding to the allowable visit window, to look for increases $>$ 2 g/dL over 3 weeks
- Hgb increase $>$ 4 g/dL over 4 weeks (+1 week)
 - Note: for programming purposes, a +1 week window is applied, corresponding to the allowable visit window, to look for increases $>$ 4 g/dL over 5 weeks

To identify Hgb increases that meet the increase criterion above, all Hgb values taken within [AE start date – 58 days, AE start date + 15 days] will be identified. This corresponds to identifying Hgb values that occurred 4 weeks before the [AE start date – 30 days, AE start date +15 days] window of interest. HemoCue Hgb and central laboratory Hgb values will then be evaluated separately to identify increases, so that HemoCue and central laboratory Hgb values are not compared to each other to identify an increase.

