For HemoCue Hgb and separately for central laboratory Hgb values, if there is a Hgb value (or daily Hgb average) within the [AE start date – 30 days, AE start date +15 days] window and an earlier Hgb value (or daily Hgb average) that is within the larger [AE start date – 58 days, AE start date + 15 days] window, and the amount of time between the two Hgb values is:

- Between 1 day and 3 weeks, inclusive, then the Hgb values will be compared to determine if there has been a Hgb increase $>$ 2g/dL.
- Between 15 days and 5 weeks, inclusive, then the Hgb values will be compared to determine if there has been a Hgb increase $>$ 4g/dL.

Unscheduled Hgb values will also be used in the assessment of secondary to excessive erythropoiesis following the guidance specified in Section [10.6.3](#) for unscheduled Hgb values and

Adverse Events

multiple Hgb values on the same date.

Pre-defined Lists of AE Preferred Terms Corresponding with Each AESIThrombosis and/or tissue ischemia secondary to excessive erythropoiesis

- Narrow SMQ: Embolic and thrombotic events, arterial
- Narrow SMQ: Embolic and thrombotic events, venous
- Narrow SMQ: Embolic and thrombotic events, vessel type unspecified and mixed arterial and venous
- Broad SMQ: Thrombophlebitis
- Additional Preferred Terms:
 - Vascular access site occlusion
 - Vascular access site complication
 - Retinal vascular occlusion
 - Administration site ischaemia
 - Anterior segment ischaemia
 - Application site ischaemia
 - Biliary ischaemia
 - Bone marrow ischaemia
 - Brain stem ischaemia
 - Catheter site ischaemia
 - Cerebellar ischaemia
 - Cerebral ischaemia
 - ECG signs of myocardial ischaemia
 - Gastrointestinal ischaemia
 - Graft ischaemia
 - Hepatic ischaemia
 - Implant site ischaemia
 - Infusion site ischaemia
 - Injection site ischaemia
 - Intestinal ischaemia
 - Ischaemia
 - Macular ischaemia
 - Medical device site ischaemia
 - Myocardial ischaemia
 - Peripheral ischaemia
 - Renal ischaemia
 - Retinal ischaemia
 - Spinal cord ischaemia
 - Stoma site ischaemia
 - Subendocardial ischaemia
 - Uterine ischaemia
 - Vaccination site ischaemia
 - Vestibular ischaemia
 - Cerebral small vessel ischaemic disease
 - Colitis ischaemic
 - Delayed ischaemic neurological deficit
 - Hypoxic-ischaemic encephalopathy
 - Ischaemic cardiomyopathy
 - Ischaemic cerebral infarction
 - Ischaemic contracture of the left ventricle
 - Ischaemic enteritis
 - Ischaemic gastritis
 - Ischaemic heart disease prophylaxis

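### The 58-day Hgb look-back for the thrombosis AESI cuts off part of the extra visit-tolerance week in the >4 g/dL rule; a 5-week pair interval needs 65 days

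*SAP*

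**What the plan says.** All of the rule is in SAP Section 10.6.4.4, under AEs of Special Interest.

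- **Window for the later value.** "Thrombosis and tissue ischemia events will be considered to be secondary to excessive erythropoiesis if during the window of" day -30 to day +15 around AE start, any one of three Hgb criteria is met: a value of 13 g/dL or more, a rise of more than 2 g/dL over 2 weeks (+1 week), or a rise of more than 4 g/dL over 4 weeks (+1 week). The programming notes turn the last two into 3 and 5 weeks, to match the allowable visit window.
- **Pool of values.** "To identify Hgb increases that meet the increase criterion above, all Hgb values taken within" day -58 to day +15 are collected. The stated reason for 58 is: "This corresponds to identifying Hgb values that occurred 4 weeks before the" window of interest.
- **Pairs compared.** A later value in the day -30 to +15 window is set against an earlier one, under the condition "and an earlier Hgb value (or daily Hgb average) that is within the larger" day -58 to +15 window. For the larger rise the interval is: "Between 15 days and 5 weeks, inclusive, then the Hgb values will be compared to determine if there has been a Hgb increase" of more than 4 g/dL. For the smaller rise it is: "Between 1 day and 3 weeks, inclusive, then the Hgb values will be compared to determine if there has been a Hgb increase" of more than 2 g/dL.

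**The concern.** The week of visit tolerance was added to the pair interval but not to the look-back. The 58 days match a 4-week interval, whereas the comparison step allows 5 weeks. A later value near day -30 can therefore call for an earlier value that the pool excludes.

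The excluded lags, 29 to 35 days, are those the extra week was meant to admit. They are ordinary in Year 1: the schedule in Section 10.2.1.1 is mostly 4-weekly with the tolerance "Protocol activity (visits ±1 week, except Weeks 2 and 4 which are ±3 days", so an on-time visit followed by one that is 1 to 7 days late gives a gap of 29 to 35 days. The >2 g/dL rule cannot assess such a pair, because it stops at 21 days.

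At stake is the classification of a Tier 1 event that Section 8.2.4 compares between arms. The truncation can only remove events from this category. It cannot add any.

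**Working it through.** **Inputs (SAP Section 10.6.4.4).** Later value on day d, with d from -30 to +15 (46 days). Lag g from 15 to 35 days for the >4 g/dL rule (21 lags) and from 1 to 21 days for the >2 g/dL rule (21 lags). Earliest day allowed for the earlier value: -58.

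**The plan's own figure.** Look-back = 30 + longest lag. With 4 weeks, 30 + 28 = 58, which reproduces the stated limit and its stated reason.

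**With the programmed interval.** 5 weeks = 35 days, so 30 + 35 = 65.

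**The >2 g/dL rule.** 3 weeks = 21 days, so 30 + 21 = 51. This lies inside 58, and no pair is lost.

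**Pairs lost under the >4 g/dL rule.** A pair is lost when d - g < -58, that is, when g > d + 58.

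| Later value on day | Lags lost | Number lost |
|---|---|---|
| -30 | 29 to 35 | 7 |
| -29 | 30 to 35 | 6 |
| -28 | 31 to 35 | 5 |
| -27 | 32 to 35 | 4 |
| -26 | 33 to 35 | 3 |
| -25 | 34 to 35 | 2 |
| -24 | 35 | 1 |
| -23 to +15 | none | 0 |

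Total lost: 7 + 6 + 5 + 4 + 3 + 2 + 1 = 28.

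- Share of all permitted pairs: 28 / (46 × 21) = 28 / 966 = 2.9%.
- Share of pairs with lags of 29 to 35 days: 28 / (46 × 7) = 28 / 322 = 8.7%.
- With a 65-day look-back: 0 of 966 lost. Full enumeration confirms that 65 is the smallest look-back that loses none.

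**The boundary is arbitrary.** A 35-day rise ending on day -23 has its earlier value on day -58 and counts. The same rise ending on day -24 has its earlier value on day -59 and does not.

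**The case against.** The strongest reply is that the criterion is nominally a 4-week rise, that 58 days covers every 4-week lag on every day of the window, and that only a programming allowance is clipped. This is correct. Even on day -30, lags of 15 to 28 days are tested. A reader might infer that the >4 g/dL rule cannot be applied early in the window, or that all lags of 29 to 35 days are missing throughout days -30 to -24 (7 × 7 = 49 pairs). Neither holds: the loss tapers, and it totals 28.

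Nor is the procedure ambiguous. The three conditions (later value in its window, earlier value in the pool, lag in range) are joined, so a programmer can implement them as written. The result is simply narrower than the 5-week interval announced.

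Several things also limit the consequence:

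- Any Hgb of 13 g/dL or more in the window already qualifies the event. A missed rise of more than 4 g/dL therefore generally has a later value below 13 and so an earlier value below 9 g/dL (13 - 4). That is possible, since Section 2.3 shows entry from 8 g/dL, but it narrows the field.
- A rise of more than 2 g/dL within 3 weeks, or another retained >4 g/dL pair, also qualifies the event. HemoCue and central laboratory series are each checked, and unscheduled values count.
- From Week 64 scheduled visits are 12 weeks apart, so affected pairs then need unscheduled values.
- The same rule applies to both arms, and Tier 1 comparisons are nominal and unadjusted. No co-primary or multiplicity-controlled conclusion depends on it.

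All of this bears on size. None of it explains why a 5-week pair interval has a 4-week look-back, and no other part of the SAP repairs the mismatch.

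**Conclusion.** The look-back and the pair interval in Section 10.6.4.4 disagree by 7 days. The extra week of the >4 g/dL rule is partly cut off for later values on days -30 to -24, and nothing else is affected. The loss is 28 of 966 day-lag pairs.

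A reader might take the 2.9% or 8.7% as the share of events missed. The SAP does not support that: the counts weight every day combination equally, whereas an event is missed only if its sole qualifying evidence is one of the excluded pairs. The event frequency cannot be derived from the document. Given the other criteria and the mainly Year 1 reach, few AESIs would be expected to change. There is likewise no basis for inferring a bias towards either arm. What can be said is that the error runs one way, towards under-identification.

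This rests on taking the 5-week interval as intended. The SAP states it in the programming note and again in the comparison step, and gives no exception for the start of the window. It is a minor correction, worth making because the rule as written does not do what it announces.

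**What to change.** In Section 10.6.4.4, change the start of the larger window from AE start - 58 days to AE start - 65 days (30 + 35) in both places: where the pool of Hgb values is defined and where the pair comparison repeats it. Change the explanatory sentence from 4 weeks to 5 weeks before the window of interest. The >2 g/dL rule needs no change.

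The cost is these text edits and the matching look-back in the program. It only widens the date range over which Hgb values are read for the derivation, and the extra pairs admitted are those the stated 5-week interval already calls for. If the sponsor did mean 58 days to govern, the two statements still have to be reconciled, by limiting the pair interval to 28 days and dropping the extra week from that rule. That would contradict the visit-window reasoning the SAP gives, so 65 days is the reading the text supports.

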10.6.4.5. Laboratory Parameters

Laboratory Parameters

 • If a laboratory value which is expected to have a numeric value for summary purposes, has a non-detectable level reported in the database, where the numeric value is missing, but typically a character value starting with '<x' or '>x' (or indicated as less than x or greater than x in the comment field) is present, the number of significant digits in the observed values will be used to determine how much to add or subtract in order to impute the corresponding numeric value. 
 ○ Example 1: 2 Significant Digits = '< x' becomes x – 0.01 ○ Example 2: 1 Significant Digit = '> x' becomes x + 0.1 ○ Example 3: 0 Significant Digits = '< x' becomes x – 1

 • If there is more than one laboratory value on the same date for the same laboratory test, then the laboratory values associated with scheduled visits will be used. Hgb summaries and analyses are an exception and should use the data handling conventions outlined in Section 10.6.3.

 • For purposes of flagging worst-case post baseline laboratory values: 
 ○ If there are multiple scheduled values on the same day, or only multiple unscheduled values on the same day, then the average of the values on that day should be used for the purpose of determining the worst-case value.

 • The following will be used to convert laboratory values from SI units to conventional units [Iverson, 2007]: 
 • MCHC and Albumin: Divide the g/L value by 10 to get the g/dL value. • Albumin corrected calcium: Divide the mmol/L value by 0.25 to get the mg/dL value. • Creatinine: Divide the umol/L value by 88.4 to get the mg/dL value. • eGFR: Multiply the mL/sec/1.73m² value by 60 to get the mL/min/1.73m² value. • Phosphate: Divide the mmol/L value by 0.323 to get the mg/dL value. • BUN: Divide the mmol/L value by 0.357 to get the mg/dL value. • Total cholesterol, LDL-C and HDL-C: Divide the mmol/L value by 0.0259 to get the mg/dL value. • Urine albumin/creatinine ratio: Multiply the mg/mmol value by 8.84 to get the mg/g value.

 • eGFR will be calculated automatically by the central laboratory using the CKD Epidemiology Collaboration (CKD- EPI) for all subjects 
CKD – EPI: $GFR = 141 \times \min(S_{cr}/k, 1)^\alpha \times \max(S_{cr}/k, 1)^{-1.209} \times 0.993^{Age} \times 1.018 \text{ [if female]} \times 1.159 \text{ [if black]}$ where: S_{cr} is serum creatinine in mg/dL, k is 0.7 for females and 0.9 for males, α is -0.329 for females and -0.411 for males, min indicates the minimum of S_{cr}/k or 1, and max indicates the maximum of S_{cr}/k or 1.
 
The demographic information used by the central laboratory for the calculation of eGFR (i.e., gender and race) will be reconciled with the demographic information contained in the eCRF to ensure consistency.

Laboratory Parameters

 • The collected lab values of eGFR, creatinine(serum), chloride(serum), UACR, 24 hour urine collection (sodium, aldosterone and creatinine), if any, will not be used in the following scenarios: 
 ○ For subjects who had a kidney transplant, these lab values taken after the kidney transplant date will not be used. ○ For subjects who started dialysis (dialysis ≥90 days, dialysis <90 days with positive adjudication, dialysis started but duration unknown), these lab values taken after the dialysis start will not be used. ○ For subjects who started dialysis (dialysis <90 days with negative adjudication), these lab values taken during the dialysis period will not be used.
Normal Range Categories, PCI Criteria Categories and Worst Case Values

 • Normal range categories are: To Low, To Normal or No Change, To High • PCI criteria categories are: To Low, To w/in Range or No Change, To High • Subjects with a missing baseline value are to be assumed to have a normal/within range baseline value. • The determination of the worst case post baseline value takes into account both planned and unscheduled assessments. • Worst case can be either High or Low. 
 ○ If a subject has both a decrease 'To Low' and an increase 'To High', then the subject is counted in both the 'To Low' and 'To High' categories. ○ If a subject was High at baseline and decreases to Low during the time interval, then the subject is counted in the 'To Low' category. Likewise, if a subject was low at baseline and increases to high during the time interval, then the subject is counted in the 'To High' category. ○ Subjects are only counted in the 'To Normal or No Change' or 'To w/in Range or No Change' category if their values are: 
 ▪ When using normal ranges: Normal at baseline and have no high and no low values; When using PCI ranges: Within range at baseline and have no high and no low values ▪ High at baseline and do not change to low ▪ Low at baseline and do not change to high

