
 • In addition to the baseline categorical values (i.e. Treatment, Current ESA use, Region) that will be adjusted in the co-primary MACE analysis, additional covariates will be included in the Cox Proportional Hazards model: 
 ○ Continuous variables: baseline Hgb, baseline Age, baseline eGFR, logarithm of baseline UACR, baseline albumin ○ Binary variables: sex, history of myocardial infarction, history of stroke, history of heart failure, history of atrial fibrillation, history of diabetes ○ Non-binary categorical variable: race (Asian, Black, White, Other) • For a continuous variable, missing values will be imputed using the mean of all observed values of that variable in the overall study. For a binary variable, missing values will be imputed

Supportive Statistical Analyses

using a Bernoulli distribution with probability as the observed percentage of “Yes” (or “Female”) in the overall study. For race, missing values will be imputed as “Other”.

- This analysis will use the time to the first occurrence adjudicated MACE endpoint, and will use the time period for follow-up of CV endpoints as described in Section 10.6.4.
- The HR, associated two-sided 95% CI and one-sided non-inferiority and superiority p-values from this supportive analysis will be included on a forest plot with the co-primary MACE results.

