The percentage of time Hgb is ≥ 12 g/dL and the percentage of time Hgb is ≥ 12 g/dL for subjects with at least one Hgb ≥ 12 g/dL during the MP and the EP will be calculated using the Rosendaal method as described in Section 8.1.1.2. The percentage of time Hgb is ≥ 12 g/dL during the MP and the EP will be summarized using mean, standard deviation, minimum, P25, median, P75, and maximum by treatment group. This summary will be presented using evaluable Hgb values only (see Section 10.6.3).

Iron Parameters

Hepcidin, ferritin, and total iron on-treatment values will be log-transformed (see Section 10.5.2) and summarized using geometric mean, coefficient of variation, minimum, P25, median, P75, and maximum for each scheduled visit by treatment group. Graphical summaries will be provided.

TSAT and TIBC on-treatment values will be summarized using mean, standard deviation, minimum, P25, median, P75, and maximum for each scheduled visit by treatment group. Graphical summaries will be provided.

Percent change from baseline in log-transformed (see Section 10.5.2) hepcidin, ferritin, and total iron on-treatment values will be summarized using geometric mean, 95% confidence interval, minimum, P25, median, P75, and maximum for each scheduled visit by treatment group. Graphical summaries will be provided.

Change from baseline in TSAT and TIBC on-treatment values will be summarized using mean, standard deviation, minimum, P25, median, P75, and maximum for each scheduled visit by treatment group. Graphical summaries will be provided.

Average quarterly TSAT while on treatment will be summarized by presenting average TSAT values by quarter (see Section 10.6.3). Summaries will include mean, standard deviation, minimum, P25, median, P75, and maximum by treatment group. Graphical summaries will be provided.

Average quarterly ferritin while on treatment will be summarized by presenting average ferritin values by quarter (see Section 10.6.3). Summaries will include geometric mean, coefficient of variation, minimum, P25, median, P75, and maximum by treatment group. Graphical summaries will be provided.

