Total cholesterol, LDL-C (direct), and HDL-C on-treatment values will be log-transformed and summarized using geometric mean, CV, minimum, P25, median, P75, and maximum for each scheduled visit by treatment group. Graphical summaries will be provided.

Percent change from baseline in log-transformed total cholesterol, LDL-C (direct), and HDL-C on-treatment values will be summarized using percent change geometric mean, 95% confidence interval, minimum, P25, median, P75, and maximum for each scheduled visit by treatment group. Graphical summaries will be provided.

Renal Function

Renal function parameters for this study include eGFR, serum creatinine and UACR. These values are collected according to the schedule outlined in the Time and Events table (see Section 10.2.1). Renal function parameter values follow the derivation guidelines for laboratory values outlined in Section 10.6.4. eGFR summaries were described in the additional secondary safety analyses section (see Section 8.2.2). The UACR summaries below will summarize log-transformed values.

Post-randomization serum creatinine values will be summarized using mean, standard deviation, minimum, P25, median, P75, and maximum for each scheduled visit by treatment group.

On-treatment UACR values will be summarized using geometric mean, CV, minimum, P25, median, P75, and maximum for each scheduled visit by treatment group.

Post-randomization serum creatinine change from baseline values will be summarized using mean, standard deviation, minimum, P25, median, P75, and maximum for each scheduled visit by treatment group.

On-treatment UACR change from baseline values will be summarized using percent change geometric mean, 95% confidence interval, minimum, P25, median, P75, and maximum for each scheduled visit by treatment group.

The number and percent of subjects transitioning to dialysis during the study will be provided by treatment group.

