8.2.5.2. Planned Clinical Laboratory Safety Display Details

Clinical Chemistry

Continuous on-treatment values (see Section 10.4.1) will be summarized using mean, standard deviation, minimum, P25, median, P75, and maximum for each scheduled visit and for baseline and end of treatment (see Section 10.6.4) by treatment group..

Continuous on-treatment change from baseline values will be summarized using mean, standard deviation, minimum, P25, median, P75, and maximum for each scheduled visit and for end of treatment (see Section 10.6.4) by treatment group.

The number and percentage of subjects with on-treatment worst case laboratory results relative to PCI criteria (see Section 10.8.1) which are post-baseline relative to baseline will be summarized by laboratory test, category and treatment group. See Section 10.6.4 for additional information on worst case values and PCI categories

Hematology

The displays presented for clinical chemistry laboratory values will also be presented for the hematology laboratory tests listed in Section 8.2.5.

Other Laboratory Tests

The displays presented for clinical chemistry laboratory values will also be presented for the other laboratory tests listed in Section 8.2.5. For reporting purposes, iron parameters will be included in other laboratory tests for PCI displays.

On-treatment hsCRP values will be log-transformed (see Section 10.5.2) and summarized using geometric mean, coefficient of variation, minimum, P25, median, P75, and maximum for each scheduled visit by treatment group.

Percent change from baseline in log-transformed (see Section 10.5.2) on-treatment hsCRP values will be summarized using geometric mean, 95% confidence interval, minimum, P25, median, P75, and maximum for each scheduled visit by treatment group.

Hepatobiliary (Liver)

Please refer to the protocol for details of liver chemistry stopping criteria.

Liver monitoring/stopping events will be summarized by treatment group.

Hepatobiliary laboratory abnormalities will be summarized by treatment group.

Medical conditions for subjects with liver stopping events and substance use for subjects with liver stopping events will be listed.

A scatter plot of maximum on-treatment ALT values versus baseline ALT values will be produced.

A scatter plot of maximum on-treatment total bilirubin (xULN) versus maximum on-treatment ALT (xULN) values will be produced.

All Laboratory

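### The non-detect rule can return zero or a negative value for laboratory parameters that the SAP then log-transforms; a strictly positive substitution should be fixed.

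*SAP*

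**What the plan says.** SAP Section 10.6.4.5 covers laboratory results that should be numeric but are reported only as below or above a limit. It says that "the number of significant digits in the observed values will be used to determine how much to add or subtract" and gives three examples:

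- "2 Significant Digits = '< x' becomes x – 0.01"
- "1 Significant Digit = '> x' becomes x + 0.1"
- "0 Significant Digits = '< x' becomes x – 1"

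Several laboratory parameters are then analysed on the log scale:

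- Section 8.1.2.2, iron parameters: "Hepcidin, ferritin, and total iron on-treatment values will be log-transformed".
- Section 8.2.5.2, other laboratory tests: "On-treatment hsCRP values will be log-transformed".
- Section 8.2.3.2, renal function: "The UACR summaries below will summarize log-transformed values". The same section logs total cholesterol, LDL-C and HDL-C, and refers both lipid and renal parameters to the derivation rules of Section 10.6.4.
- Section 7.2.2, supportive expanded covariate adjusted analysis: the Cox model includes the "logarithm of baseline UACR". A missing continuous covariate is replaced by the mean of the observed values in the whole study.

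Section 10.5.2.2 sets out how geometric means and percent changes are computed. It takes a plain logarithm and states no offset, no floor and no rule for a value of zero or below.

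**The concern.** The imputation step and the log step do not fit together for every input that the first one allows. Subtracting a whole reporting unit from a limit that is itself one unit or less leaves nothing positive to log. The values concerned are by definition the lowest, so their loss is not random. A geometric mean computed without them is too high. If one arm lowered an analyte more than the other, that arm would lose more values.

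In the expanded MACE model the risk is miscoding. A subject with almost no albuminuria could be given the average value of a prognostic covariate. The SAP does not say whether an undefined logarithm counts as missing, so the choice would fall to the programmer.

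The wording is also faulty. No reported number has zero significant digits, and the three examples make sense only if the count refers to decimal places.

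**Working it through.** **The rule as a formula.** Let d be the number of decimals in the observed values and x the reported limit. The imputed value is x − 10^(−d). For d = 2, 1 and 0 the step is 0.01, 0.1 and 1, which reproduces the three amounts in Section 10.6.4.5.

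**Results for a value below x**

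| Decimals in observed values | Limit x | Imputed value | Natural log |
|---|---|---|---|
| 0 | 0.5 | −0.5 | undefined |
| 0 | 1 | 0 | undefined |
| 0 | 2 | 1 | 0 |
| 0 | 5 | 4 | 1.386 |
| 1 | 0.1 | 0 | undefined |
| 1 | 0.2 | 0.1 | −2.303 |
| 1 | 1.0 | 0.9 | −0.105 |
| 2 | 0.01 | 0 | undefined |
| 2 | 0.1 | 0.09 | −2.408 |

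The log fails when x ≤ 10^(−d) and exists otherwise. The step follows the precision of the observed values, not the way the limit is printed. A limit of 1 therefore fails with whole-number results and works with one-decimal results.

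**Share of the limit that is imputed.** This is 1 − 10^(−d)/x. With no decimals, limits of 2, 5 and 20 give 0.5, 0.8 and 0.95. With two decimals, a limit of 0.20 also gives 0.95. The share depends on the limit and the precision together.

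**Effect on a geometric mean if values are lost.** The SAP gives no limits or non-detect rates, so what follows rests on assumptions. Take log values as normal with standard deviation s, and drop the lowest fraction p. The mean log rises by s·φ(z_p)/(1 − p), and the geometric mean is multiplied by the exponential of that amount. With s = 1.2:

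- p = 1%: φ(z_p) = 0.0267; 1.2 × 0.0267 / 0.99 = 0.032; exp(0.032) = 1.03, or +3%.
- p = 5%: φ(z_p) = 0.1031; 1.2 × 0.1031 / 0.95 = 0.130; exp(0.130) = 1.14, or +14%.

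Over a wider assumed range (s from 1.0 to 2.0, p from 1% to 10%), simulated log-normal data gave geometric means of 1.03 to 1.48 times the true value when non-detects were dropped, and 0.98 to 1.03 times when they were set to x/2.

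**Percent change.** Section 10.5.2.2 needs both the baseline log and the visit log. Losing subjects whose visit value is undetectable removes large falls and pushes the estimate up. Losing subjects whose baseline is undetectable tends to remove rises and pushes it down. The net direction is not determined.

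**Covariate.** If the undefined log UACR is treated as missing and mean-filled, the same assumed range of p moves the affected values up by about 1.9 to 2.7 standard deviations. The covariate's variance falls to between 0.93 (1% affected) and 0.64 (10% affected) of its true value.

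**The case against.** The strongest reply is that nothing in the SAP shows the failure will ever occur. It gives no assay limit, reporting precision or non-detect rate for any logged parameter. For ferritin, the management thresholds of 100 and 800 ng/mL in Section 10.6.3.2 lie far from a one-unit limit. That stands. A reader might infer that the lowest values will be lost; the document supports only that they could be.

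Three further inferences go too far:

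- That subjects with undetectable UACR leave the expanded MACE model. Under Section 7.2.2 a missing continuous covariate is filled with the study mean, so the subject stays and is at most miscoded.
- That percent changes are biased upward. The direction depends on which of the two values is lost.
- That the imputed share of the limit is set by decimals alone. The limit matters as well.

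It is also fair to say that little depends on these outputs. The iron, lipid and UACR summaries are exploratory with no testing planned, hsCRP is a descriptive safety display, and log UACR enters one supportive model. Filling a few baseline values without regard to arm should barely move the treatment hazard ratio, and no effect on it has been shown. Finally, x/2 is one convention among several; the defect itself requires only that the substitute be positive.

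None of this removes the mismatch. The SAP states a rule that can produce values its next step cannot use, and whether it does so depends on assay details that the SAP does not give.

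**Conclusion.** The point holds as a conditional defect of low severity. The rule in Section 10.6.4.5 returns zero or a negative number whenever a parameter's limit is at or below one unit of its observed precision, and the log-scale analyses have no safeguard.

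Its practical size is unknown and may be nil. The overstatement of 3% to 14% is a within-arm figure for the geometric mean only. It rests on an assumed log SD of 1.2, on 1% to 5% of values being lost, and on log-normality; it says nothing about a between-arm difference.

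A reader might fear for the primary results, but the documents give no ground for that. The co-primary Hgb ANCOVA uses treatment, baseline Hgb, ESA use and region, and the co-primary MACE model uses treatment, ESA use and region. Neither contains a logged laboratory value.

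**What to change.** Amend Section 10.6.4.5 in three respects:

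1. For parameters analysed on the log scale, replace the rule for results below x with a strictly positive substitution, for example x/2, whatever the number of decimals.
2. State that no imputed value may be 0 or below.
3. Change the term significant digits to decimal places.

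With a positive substitute, log baseline UACR is always defined for a non-detect, so the question of mean-filling in the expanded MACE model does not arise for these subjects. The cost is one line of SAP text and the matching line of program code. No data collection and no co-primary analysis changes.
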